A thorough discussion of the trial, signing the informed consent form, and confirmation of inclusion/exclusion criteria will be completed during the baseline visit (T_0). Consenting may be done in-person on paper or using e-consent. If utilizing econsent, participants will be presented a consent form ahead of time, and upon signature in the REDCap system, participants will receive a pdf of what they 'signed' electronically via REDCap. A pdf will also be generated for study records. T₀ may occur on the same day as T₁ if the patient has already completed the main DISCOMS study and is within the window for the Month 36 visit. There will be one phone call (P1), conducted by the study coordinator, at 30 Months post-enrollment in the original DISCO MS trial. On this phone call, the participant will be asked about any new or ongoing adverse events, changes to medications, and any symptoms suggesting a potential relapse. If the participant joins the Extension study after they already passed 30 Months post-enrollment in the original DISCO MS trial, they will not do P₁. Those who have already exceeded 30 months since starting the primary DISCOMS trial will have the equivalent of the phone assessment at the T_0 visit. Participants will come in for 1 additional study visit; T_1 at 36 Months post-enrollment in the original DISCO MS trial. During T₁, patients will undergo a blinded EDSS exam and relapse assessment, vitals, complete an SDMT assessment, and will complete all PROs/comorbidities. All PROs/comorbidities may be completed on paper in person or remotely via the electronic platform within the visit window, based on site and patient needs. Participants will also undergo a standard of care MRI scan of the brain at T1, within 60 days before and 120 days after the study visit. Participants who have already exceeded 12 months from the end of the primary trial will still be recruited and simply do the T₁ visit at their earliest convenience. The maximum window will be 30 months after completion of the primary study, or 54 months since starting DISCOMS. Participants should always be brought in as close to 36 months as possible. Some participants' final study visit for the original DISCO MS study will be at 18 Months. For these subjects, the P₁ visit will occur 24 Months after enrollment in the original study, and T₁ will occur 30 Months after enrollment in the original study.

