All participants will undergo the T_1 visit, which will include a formal, blinded relapse assessment by the Examining Physician (EDSS rater) in conjunction with the PI (see section E). Prior to enrollment, the enrolling physician will certify, based on their personal review of the prior MRI scans and/or reports which will include data from the 24 month primary DISCOMS trial, that the scans have been stable for a minimum of 4.5 years (review of minimum of two scans, although it could be more, separated by at least 4.5 years). MRI scans at T_1 , 36+ months after onset of participation in the primary trial, will be performed as per usual SOC, paid for by patient insurance, at whatever site is normally used by the patient (preferably the same scanner each time, and preferably the same scanner as the investigation site), and should be done on a MRI machine with magnet 1.5 Tesla or greater, with and without contrast. Gadolinium may be withheld at the discretion of the PI or request of the patient. The window for T_1 MRIs will be 60 day before or 120 days after the T_1 study visit, and will be analyzed by a central, board-certified, blinded neuro-radiologist for new activity compared to prior scans. All MRI scans will be read locally for safety and clinical purposes, and PIs will communicate any significant MS or non-MS findings to the primary neurologist (should they not be the primary neurologist). Any new lesion documented on the T_1 MRI scan will prompt delivery of a notice within 48 hours, to the PI, that the patient has achieved the endpoint of the study, with a description of relevant findings.

In the event of a suspected relapse, the patient will be instructed to contact their physician and the study coordinator at their local site within 48 hours of new symptoms and come in for an unscheduled visit and relapse evaluation within seven days of symptom onset. Use of corticosteroids will be at the discretion of the patient and the local PI or other physician. Use of systemic steroids to treat MS symptoms will be concluded to be a Protocol-defined relapse. As at scheduled visits, the determination of a relapse at an unscheduled visit will be made by the blinded EDSS examiner, who will perform the EDSS and only then receive information about recent clinical history.

D. Risks/Safety:

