It is possible that data from the primary DISCOMS trial will become available before the end of participation by those in the extension trial. Whatever the outcome: if the data will conclude that those who have discontinued DMT have an inferior outcome compared to those who continued DMT or if the trial concludes there is no evidence of a difference to date, all participants still in the extension trial will be given results of the primary DISCOMS study by telephone, or email if they do not answer the phone, within two weeks of generation of the primary outcome data. They will be asked to verbally (or by email) consent to continue participation at that time. At least three attempts will be made to contact participants by a combination of the two techniques, phone or email. These attempts and the participants' responses will be documented in the source documents and electronic data capture system. As there is only a single visit at 12 months after signing the consent for the extension trial, no reconsent beyond this will be performed. This verbal/email reconsent possibility will be included in the original consent of the extension trial. Regardless of their treatment decision after learning the results of the primary DISCOMS trial, they will be followed to the end of the extension trial with the treatment as they choose in response to the primary results.

Primary endpoints will be defined as either:

1. "Relapse" will be defined as the appearance of new neurological symptoms or worsening of pre-existing neurological symptoms lasting at least 48 hours in a subject who had been neurologically stable or improving in the previous 30 days *and* accompanied by objective change in the neurological examination corresponding to that symptom (worsening of 0.5 point on the EDSS or worsening by 1.0 or more points on the pyramidal, cerebellar, brainstem or visual functional system score). Fatigue or subjective cognitive worsening, alone or in combination, will not be considered a "Protocol defined relapse."

Each Relapse event will be categorized on CRFs as one of the below:

• Protocol defined relapse

A relapse seen within 7 days of onset, independently and blindly observed as a change in EDSS by the Examining Clinician. This relapse is defined as: the appearance of a new symptom or worsening of an old symptom, attributable to MS; accompanied by a change in the neurologic examination attributed to those

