study. Aim #2 will be mostly descriptive and assesses progression of disability as noted on the EDSS, and this will be defined as an increase of at least one point, confirmed at 6 months, for those with a baseline EDSS \leq 5.5, or a change of at least 0.5 for those with EDSS of 6.0 or greater at baseline. The estimates of the population from the origin of the study will be model based since participants in the extension study must by criteria have not had progression over the initial period of follow-up. Nevertheless, we will have the proportion at the end of the formal DISCOMS study and can apply the successive failure rates using conditional probability to obtain an overall estimate of the progression rate after 2 or 3 years and further can compare the post DISCOMS experience between the two arms given the participants were free of events at entry into the Extension study. Outcomes assessed will include % of patients with progression in each group as compared to the final EDSS in DISCOMS, and mean change in EDSS in each group overall (via the extension period. The latter analyses will help identify if the rate is increasing over time or if the rate is relatively stable over time.

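### Aim 2 requires a 6-month confirmation of EDSS progression that a single-visit extension cannot supply, and its chained rate assumes a progression-free entry criterion that does not exist

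*Combined protocol and SAP*

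**What the plan says.** Section III.F, Aim #2, defines progression on the EDSS. For a baseline of 5.5 or lower, "this will be defined as an increase of at least one point, confirmed at 6 months". The sentence continues "or a change of at least 0.5 for those with EDSS of 6.0 or greater at baseline", without saying whether confirmation applies there too. The percentage progressing is taken "as compared to the final EDSS in DISCOMS".

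The extension has one scheduled examination. Section III.C: "Participants will come in for 1 additional study visit", namely T1. Section III.D: "As there is only a single visit at 12 months after signing the consent for the extension trial". In Table 2 the EDSS row is marked only at T1 and at unscheduled visits. T0 has no EDSS of its own, and P1 is a telephone call. Section III.C ties the unscheduled visit to suspected relapse: the patient is to "come in for an unscheduled visit and relapse evaluation within seven days of symptom onset". T0 and T1 may fall on the same day "if the patient has already completed the main DISCOMS study and is within the window for the Month 36 visit".

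Aim #2 then plans to carry the DISCOMS progression proportion forward by conditional probability to 2 or 3 years, on the ground that "participants in the extension study must by criteria have not had progression over the initial period of follow-up".

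**The concern.** The outcome needs two examinations about six months apart, the first showing a rise from the final DISCOMS score. The schedule supplies one. The plan does not say how to score a rise that cannot be confirmed, so the analyst would have to choose after seeing the data: score it as no progression, drop confirmation in one stratum, or drop it in both. These choices give different percentages from the same records, and only some match the written definition.

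The chaining step has a separate fault. A conditional probability of progressing in the extension, given no progression in DISCOMS, must be estimated in people who had not progressed. The plan says the entry criteria guarantee this. If they do not, the conditional rate comes from a mixed group.

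Disability progression is one of three specific aims and is framed as a no-worse question, so its headline percentage should mean what its definition says.

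**Working it through.** **Plan's own figure.** The plan gives no rate, sample size or power for Aim 2. Its only worked test, 10/50 against 3/50 by Fisher's exact test, concerns failure proportions. It reproduces (one-sided p = 0.0357, stated as 0.036), and this point does not depend on it.

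**Step 1: can a rise be confirmed?** Inputs are Table 2 and section III.C.
- Scheduled EDSS in the extension: 1 (T1). Scheduled EDSS at least six months after T1: 0.
- T1 at month 36 would need confirmation at 36 + 6 = month 42. Across the T1 window (months 35 to 54) that is months 41 to 60. Those who finished DISCOMS at 18 months have T1 at month 30 and would need month 36. No such visit exists.
- For T1 itself to confirm a rise, an unscheduled EDSS must have shown it by 36 - 6 = month 30. Entrants whose T0 and T1 coincide have no earlier extension EDSS. In December 2020, 49/123 = 40% of completers were already at least 12 months past DISCOMS. That is the recruitment pool, not an enrolment count.

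**Step 2: how much is counted?** The documents give no EDSS distribution or progression rate, so all inputs here are assumptions, and unconfirmable rises are scored as no progression. Let f be the share at EDSS 6.0 or greater, w the share with a qualifying rise at T1 (10% overall), and u the share of rises already recorded at least six months before T1.
- Confirmation in the lower stratum only, equal w in both strata: counted = f·w + (1 - f)·w·u. With u = 0: 0.2 × 0.10 = 2% and 0.4 × 0.10 = 4%. With u = 0.1: 2.8% and 4.6%.
- Same reading, unequal strata, u = 0. With f = 0.4 and rates 17.5% and 5%, the overall rate is 0.4 × 0.175 + 0.6 × 0.05 = 10%, of which 7 points are counted. With f = 0.2 and rates 30% and 5%, it is 0.2 × 0.30 + 0.8 × 0.05 = 10%, of which 6 points are counted.
- Confirmation in both strata: counted = w·u = 0% (u = 0) or 1% (u = 0.1).
- Confirmation dropped: 10%.

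**Step 3: is progression-free entry a criterion?** Section III.B excludes relapse or a new MRI lesion during DISCOMS and a changed drug assignment. Its inactivity requirement concerns inflammatory activity, which the Background separates from progression. Sections II and III.C define successful completion by the same events. SPMS and PPMS are eligible, and an EDSS change of at least 1.0 over two years appears only to define progression of MS. Nothing excludes EDSS progression.

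**Step 4: size of the chaining error.** The plan calls the estimate model based without giving the model, so simple multiplication is assumed: P = 1 - (1 - p)(1 - q). If a share s of extension participants had already progressed, with later risk q1 against q0 in the rest, the error is (1 - p)·s·(q1 - q0). The assumed grid is p 0.10 to 0.20, s 0.05 to 0.20, q0 = 0.05, q1 0.00 to 0.20.
- Maximum: 0.9 × 0.2 × 0.15 = +2.7 points. Minimum: 0.9 × 0.2 × (-0.05) = -0.9 points. Zero when q1 = q0.
- With s no greater than p, the range is -0.8 to +2.4 points.
- 95% half-width of P, with 260/2 = 130 per arm in DISCOMS and 50 in the extension: 1.96 × √[(1 - q)²p(1 - p)/130 + (1 - p)²q(1 - q)/50] = 7.7 points (p = 0.10, q = 0.06) and 8.7 points (p = 0.20, q = 0.08).

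**The case against.** The strongest reply is that much of Aim 2 survives. Mean EDSS change and change-score differences need no confirmation. The Aim #3 paragraph already plans between-group tests of dichotomized EDSS change and states no confirmation rule. If confirmation applies only at 5.5 or lower, the 6.0-or-greater stratum can be scored in full at T1. Unscheduled visits carry an EDSS. T1 can also confirm a rise first seen at the last DISCOMS visit, which bears on the overall 2- to 3-year rate. Aim 2 is secondary and largely descriptive, and the chaining error is below sampling error.

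All of this is right, but it limits the defect without removing it. The Aim #3 paragraph gives no EDSS cut-points, so it does not replace the Aim #2 definition. An unscheduled visit helps only if it precedes T1 by six months. One used as a final visit on leaving the study, which Table 2 allows, has no later EDSS to confirm it. A rise present at DISCOMS exit is already in the reference score for the extension percentage.

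A reader might infer that no part of the percentage can be produced, or that most worsening will be missed. The documents support neither as a general statement. The first depends on confirmation applying to both strata. The second holds on that reading, but on the other reading it depends on an EDSS mix and stratum rates that the documents do not give; with unequal strata, 6 or 7 of 10 points are counted.

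**Conclusion.** The point stands and should be fixed. As written, the percentage progressing cannot be produced at EDSS 5.5 or lower, or in either stratum if confirmation covers both, except for rises recorded at an unscheduled visit at least six months before T1. The mismatch follows directly from the definition and the visit schedule and rests on no assumption. Its numerical effect does rest on assumptions: a 10% rate of rises at T1 can be reported as anything from 0% to 10%, depending on the scoring choice, the EDSS mix and the stratum rates.

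The sentence on progression-free entry is wrong on the face of the criteria, but its consequence is minor, of uncertain sign, and nil if prior progressors carry the same later risk. A reader might infer that the chained estimate is seriously biased; the illustrative grid does not show that. Neither fault touches the primary outcome or mean EDSS change.

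**What to change.** - Define the extension outcome in both strata as unconfirmed EDSS worsening at T1 from the final DISCOMS EDSS, keeping the 1.0 and 0.5 thresholds. Label it unconfirmed, report it by stratum and pooled, and list separately any rise confirmed through an earlier unscheduled visit. Use the same definition for the dichotomized EDSS test in the Aim #3 paragraph, and keep mean EDSS change alongside.
- Correct the sentence on entry so that it states what section III.B excludes: relapse, new MRI lesion and changed assignment.
- From existing DISCOMS data, flag EDSS progression at exit on the same unconfirmed definition against the DISCOMS baseline. A rise first seen at the final DISCOMS visit then counts as progression at exit, and T1 shows whether it was sustained. Compute the conditional rate only in those not flagged. Chain it only to a DISCOMS rate on the same definition; otherwise report the two periods separately.

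The cost is SAP wording and one derived flag, with no new visits. The price is noise: if 20% to 50% of single-visit rises would not have been confirmed (assumed), a confirmed rate of 10% would appear as 0.10/0.8 = 12.5% to 0.10/0.5 = 20%. If no matching DISCOMS rate can be derived, the chained 3-year estimate is lost.

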To address the above gaps in knowledge, we designed and are close to finishing an original 2-year, randomized, controlled 1:1 RCT (continue vs discontinue), rater-blinded DMT discontinuation study (DISCOMS, NCT#: 03073603). The last of 260 patients was enrolled on February 4, 2020. Last patient, last visit will be in August 2021 (note, not all will be followed for two years, with shortest final follow-up at 18 months in a minority of late enrollees). While this is the first RCT of DMT discontinuation, others are underway in France (NCT03653273) and The Netherlands (NCT04260711). Among focus groups employed during the operation of DISCOMS, it was very clear that one of the main limitations of the study was relatively short duration of the follow-up. Herein we propose to address this limitation with a non-randomized, yet rater-blinded protocol to extend the follow-up of 100 participants from the original DISCOMS cohort by at least 12 months. In essence, the first 100 participants from the DISCOMS primary study who have already successfully completed the primary DISCOMS study (i.e. did not fail on the primary outcome of a new relapse or Brain MRI lesion), retained their original drug assignment (continue or discontinue) at the end of their participation in DISCOMS, and agree to participate in the extension will be included for a minimum of 12 more months of follow-up as assessed at a single visit. This is a pragmatic clinical trial, based on real world patterns of patient decision-making. As such, study visits will be attached to routine office visits when possible, and the patient/their insurance will be responsible for payment of standard of care aspects related to the study. This will include drug costs, the annual brain MRI scans at year one, and all routine safety monitoring as would be obtained in a typical office setting for that individual medication. The funding agency, EMD Serono (a biopharmaceutical business of Merck Pharmaceuticals KGaA), will be responsible financially for all research aspects, including data acquisition, all research personnel, and all regulatory review. In addition, while this is a discontinuation trial, all patients will be aware of their medication assignment, while observers of the main outcomes (relapses, MRI changes and the EDSS) will be blinded.

III. Research Methods

A. Outcome Measure(s):

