- a. **Specific Aim 1:** The primary outcome being measured is safety, i.e. is there a significantly increased risk of new inflammatory disease activity, as manifested by either a new MS relapse (Protocol defined, see below) and/or a new brain MRI lesion, in those who discontinue MS DMTs vs those who continue. We have specifically chosen inflammatory markers of disease activity because that is what the MS DMTs have been shown to have greatest impact upon. As inflammatory disease activity may be manifested clinically as a relapse, or radiographically as a new MRI lesion, we have chosen a combined primary outcome measure. In addition, it is a measure which will record the mildest manifestations of new inflammatory activity, i.e. should be a sensitive marker, which is important for a safety investigation.
- b. Specific Aim 2: The EDSS is a commonly used assessment that allows clinicians to objectively measure changes in a patient's symptoms by using unbiased raters.⁷⁶ This assessment will be collected at all time-points and will be used to measure changes in patients' symptoms over the course of the study and will be used to help define 'relapse', i.e. will require a change on examination. The measure used in this study will be based on the Kurtzke Functional System Scoring (FSS)/EDSS. This will also allow us to compare the change in disability over

the duration of the trial in those who were able to maintain their treatment assignment without inflammatory activity.

- c. Specific Aim 3: The PROs being collected in this project are:

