This will be a non-randomized, rater-blinded pragmatic trial, which is an extension of the randomized discontinuation trial (RDT)⁸², DISCOMS. While RDTs have been done in cancer^{83,84} and rheumatoid arthritis patients,⁶⁶ the original DISCOMS protocol was the first such study in MS. For this protocol, a subset of 100 subjects of the original 260 enrolled will be followed. Study sites will be limited to the top 10 recruiting sites across the United States from the DISCOMS study due to financial and cost-effectiveness issues. Those sites will have participants who have completed 18-24 months of the primary study. In practice, the vast majority, if not all, will have completed 24 months. We will explicitly include any who have completed, including those who already have exceeded 12 additional months after completion of the primary trial. Individuals who have successfully completed (retained original drug assignment and did not meet the primary endpoint of DISCOMS) the primary DISCOMS trial and are willing to retain their original drug assignment after completion and for an additional 12 months will be offered entry into the extension. The only exception to that will be individuals who continued the original drug assignment during and after the primary trial, up to 24 months, but who then had a relapse, new MRI lesion, or other MS-related reason between months 24 and 36 which resulted in their change of medication assignment. These individuals can and should be included, and counted as "failing" during the extension trial completing the Kaplan-Meier event free survival curve critical to the original hypothesis. A total of up to 100 patients will be consented and enter the extension trial, regardless of assignment, on a first come first serve basis to avoid selection biases to the extent possible. The intent is to take the first 100 who fulfill criteria and agree to participate. The plan is for a 50/50 distribution, but there may not be exactly 50 in each group. As of December 15, 2020, 123 had completed participation of the primary 24-month study, and information as to DMT use plans after finishing 2-years participation in DISCOMS was available for 84/123, 42 in each group (see Table 1 below). Notably, in the Discontinue group, 86% remained off DMT while only 60% in the Continue group plan to remain on a DMT (23/42 on the same DMT, two switching to an alternative). Overall 73% remained in the primary assignment grouping. If these ratios stay consistent as more finish DISCOMS, discontinuers will account for roughly 59% of the total enrolled in the extension trial. Also, of the 123 completers, 49 have also gone at least an additional 12 months since completion of DISCOMS, and they will be offered entry into the extension trial, should they otherwise fulfill criteria. There will be no placebo and no sham treatment. (Please see the statistics section the extension ns for power analyses discussions).

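### Aim 2 reads a trend in disability from one un-annualised EDSS change in a selected subset, so an apparent trend can arise, possibly unequally by arm, when the true rate is constant

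*Combined protocol and SAP*

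**What the plan says.** Section III.F, Aim #2, lists two outcomes: the percentage in each arm progressing relative to the last DISCOMS EDSS, and "mean change in EDSS in each group overall (via the extension period". It then adds: "The latter analyses will help identify if the rate is increasing over time or if the rate is relatively stable over time". The aim is described as largely descriptive.

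For the progression percentage, the same paragraph recognises that entrants are selected. It calls estimates from the start of the study model-based and chains extension rates onto the DISCOMS result by conditional probability. For mean EDSS change it gives no such step, no reference cohort and no division by time.

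- **EDSS in the extension.** Section III.A says of the EDSS: "This assessment will be collected at all time-points". Table 2 schedules it once, at T1; otherwise it is done only at unscheduled visits. For those rolling over, the month-24 data are the baseline.
- **Timing.** T1 is nominally 36 months after DISCOMS enrolment, with a window of one month before to 18 months after. Section III.C allows up to 30 months after completing DISCOMS.
- **Who enters.** "The last of 260 patients was enrolled on February 4, 2020"; "a subset of 100 subjects of the original 260 enrolled will be followed", from the ten top-recruiting sites, first come first served. Section III.B excludes anyone with a DISCOMS relapse or new MRI lesion and requires willingness to keep the assigned group.
- **Retention by arm.** "in the Discontinue group, 86% remained off DMT while only 60% in the Continue group plan to remain on a DMT".
- **Adjustment.** The Sample Size paragraph adjusts for baseline differences between arms, not for differences between those followed in the two periods.

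**The concern.** One interval has no trend in it. To call the rate increasing or stable, the extension change must be set against the DISCOMS change, and two things then go wrong.

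First, the interval is not fixed, so a raw mean change mixes rate with length of follow-up.

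Second, the people followed in the second period were selected partly on the first. Eligibility removes relapses, which under section III.D normally require worsening on the EDSS or a functional system score. Choosing to keep the assignment may also depend on how the person did. If it does, the two periods can differ with no change in anyone's true rate, and by different amounts in the two arms because retention differs.

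Longer-term disability after stopping DMT is one of the questions the extension is meant to inform. A false statement that the rate is rising, or stable, in one arm would mislead on it.

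**Working it through.** **The plan's own figures (Table 1).** Discontinue 36/42 = 85.7%; continue (23 + 2)/42 = 59.5%; overall 61/84 = 72.6%; discontinuers 36/61 = 59.0%. All agree with the text. The difference by arm has a two-sided Fisher p of 0.013. Coverage is 100/260 = 38%. No SD or slope for EDSS is given anywhere, so what follows rests on assumed values.

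**Step 1: raw change is not a rate.** At a constant 0.10/year, the mean change is 0.10 × 1.0 = 0.10 when T1 falls at 12 months and 0.10 × 2.5 = 0.25 at 30 months. The two-year DISCOMS change would be 0.20. The raw figure can look lower or higher than DISCOMS from timing alone. Already 49 of 123 completers were at least 12 months past DISCOMS.

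**Step 2: selection on true slope.** Let r be the share retained and d the leavers' minus the stayers' mean annual change. With constant slopes, the apparent trend against all participants is −(1 − r)d, that is −0.143d (discontinue) and −0.405d (continue). For d = 0.1 this is −0.014 and −0.040/year; for d = 0.2, −0.029 and −0.081. The sign reverses if d is negative. For the same entrants in both periods it is zero.

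**Step 3: selection on observed change.** Simulation assumptions: slope 0.10/year with no acceleration, between-person slope SD 0.15, rating-error SD 0.35, and EDSS at months 0, 24 and 36. The odds of keeping the assignment are multiplied by 0.5 (or 2) per 0.5-point worse DISCOMS change, calibrated to 60% and 86% retained. EDSS is treated as continuous, and retention stands in for entry.

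| Apparent trend per year, true trend 0 | Continue | Discontinue |
|---|---|---|
| Against all participants, odds ratio 0.5 | +0.04 | +0.01 |
| Against all participants, odds ratio 2 | −0.04 | −0.01 |
| Same entrants, odds ratio 0.5 | +0.12 | +0.04 |
| Same entrants, odds ratio 2 | −0.12 | −0.04 |

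The same-entrant figures arise because the month-24 reading ends one interval and starts the next. People selected for a low reading drift back up at T1, and people selected for a high one drift down.

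With error SD 0.25 to 0.50 and odds ratio 0.7 or 0.5, the continue-arm figures run from about 0.005 to 0.09 (all participants) and 0.035 to 0.23 (same entrants). The discontinue-arm figures run from about 0.002 to 0.035 and 0.012 to 0.085.

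**Step 4: the proposed model under both mechanisms.** A mixed model with a slope change at month 24, fitted to all DISCOMS EDSS plus T1, returns 0.00 when entry depends on observed change. When entry depends on true slope, it is off by about 0.035 to 0.04/year in the continue arm, the exact figure depending on the assumed spread of starting EDSS. The same-entrant comparison is then unbiased. Neither analysis is safe alone.

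**The case against.** - **Wording.** The plan claims only to help identify a trend, refers to analyses in the plural, and calls Aim 2 mostly descriptive. The rate may mean the progression rate, for which selection is acknowledged. This stands as a caution. But the sentence follows directly on mean EDSS change, and nothing in the plan excludes it from the trend reading.
- **Comparator.** A reader might infer that the DISCOMS reference is all 260. The plan does not say so, and the problem does not depend on it.
- **Direction.** A reader might infer that the false trend is a rise, larger in the continue arm, and so flatters staying off DMT. The documents do not support this. Leaving the continue arm meant stopping DMT for all 17 of 42 leavers, which people doing well could equally choose. No reasons are reported, and eligibility has no EDSS threshold.
- **Same entrants.** A reader might infer that restricting both periods to the same people always makes matters worse. It does so under entry on observed change; under entry on true slope it removes the bias.
- **Size.** With T1 spread evenly over 12 to 30 months (assumed) and change annualised, the continue-arm figure against all participants falls from 0.038 to about 0.015/year. The central gap between arms is 0.038 − 0.014 = 0.024/year. The SD of a one-year change under these assumptions is √(0.15² + 2 × 0.35²) ≈ 0.52, so with 59 and 41 people the standard error of the arm difference is 0.52 × √(1/59 + 1/41) ≈ 0.11. The bias may well be below one standard error. That limits its weight but does not remove it.
- **Retention data.** The 86% and 60% come from 84 of 123 completers and partly record plans. They are not entry rates.

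**Conclusion.** The concern holds in a limited form. As written, Aim 2 attaches a statement about the rate over time to a mean change that is not a rate, comes from one interval, has no named comparator, and is measured in a subset selected partly on the earlier period. A false trend, possibly unequal by arm, can follow with a constant true rate.

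Under the central assumptions its size is about 0.04 v 0.01/year against all participants and 0.12 v 0.04/year against the same entrants. The largest exceeds the assumed true slope of 0.10. Sign and size rest on the assumed slope, error and reason for leaving, none of which the documents give; under entry on true slope the same-entrant figure is about zero. The documents therefore support saying that the trend is not identified by the planned summary, but not that it is biased in a known direction. The change is worth making because it alters what Aim 2 can conclude.

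**What to change.** In section III.F, Aim #2:

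1. Delete the statement that mean change identifies a trend. Keep mean change as a description, annualised by each person's actual interval.
2. Estimate the trend with a mixed model of EDSS using all DISCOMS participants' visits, including those who do not enter the extension, plus T1. Include actual time, a slope change at DISCOMS exit, and arm by slope terms. Report the slope change per arm and its difference with 95% confidence intervals.
3. Beside it, as a sensitivity analysis, report the annualised change in both periods for the same entrants. Tabulate entrants against non-entrants on DISCOMS EDSS change, by arm.
4. State that the model assumes entry depends only on observed data, and that if entry depends on true slope it can be off by about 0.035 to 0.04/year under the values above.

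The cost is SAP wording, one further model and one table. It assumes that the DISCOMS EDSS visits are available for all participants, and it needs no new visits. The price is a more cautious statement about trend.
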